#### 2 STUDY OBJECTIVES

- **2.1** Primary Objectives
- 2.1.1 Develop IntelliCare and optimize its functionality through laboratory and field usability testing.
- 2.1.2 Develop the machine learning models and algorithms that will continuously learn from user interactions with IntelliCare to provide intervention recommendations and motivational messaging.
- 2.1.3 Conduct a randomized controlled trial (RCT) comparing 8 weeks of IntelliCare with the machine learning component to 8 weeks of IntelliCare without the machine learning component for the treatment of depression and anxiety. Participants will be evaluated at baseline, week 4, week 8, and at 3- and 6-month post-treatment follow-ups. It is hypothesized that 1) IntelliCare with the recommendations, in contrast to IntelliCare without the recommendations, will produce greater adherence and greater reductions in depressive and anxiety symptoms and 2) IntelliCare with coaching will produce greater greater adherence and greater reductions in depressive and anxiety symptoms. The primary patient centered outcome will be depression/anxiety severity.
- 2.2 Secondary Objectives.
- 2.2.1 Exploration of the mediating effects of adherence markers (e.g. time in treatment, app launches, etc.) coaching variables (e.g. message frequency, timing, etc.), and psychological variables (e.g. change in self-report measures) on depression and anxiety outcomes.
- **2.2.2** Exploration of moderating variables on outcomes, such as baseline demographics, baseline characteristics.
- 2.2.3 Explore, optimize, and validate coaching methods.

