#### 3 PARTICIPANT ELIGIBILITY

- 3.1 Inclusion Criteria:
- 3.1.1 Meets criteria for clinically significant symptoms of depression and or anxiety using self-report measures used in screening for depression and anxiety as well as interviewer administered measures.
- 3.1.2 Is familiar with the use of mobile phones
- 3.1.3 Has an Android phone with at least a basic data plan and messaging plan and an operating system sophisticated enough to support the IntelliCare system
- 3.1.4 Is able to speak and read English;
- 3.1.5 Is at least 18 years of age (except in Nebraska where the age of consent is 19).
- 3.1.6 Is a United States Citizen/Resident
- **3.2** Exclusion Criteria:
- **3.2.1** Has visual, hearing, voice, or motor impairment that would prevent completion of study and treatment IRB# STU00074405 Version 11.29.2017

[figure not shown]
procedures;

- 3.2.2 Is diagnosed with a psychotic disorder, bipolar disorder, dissociative disorder, substance or alcohol dependence, or other diagnosis for which participation in this trial is either inappropriate or dangerous;
- 3.2.3 Is severely suicidal (has ideation, plan, and intent). Although procedures with back-up plans are in place for patients who develop suicidality, the highly experimental nature of this intervention makes enrollment of severely suicidal patients unethical;
- 3.2.4 Participants who have been on an antidepressant or anxiolytic medication with no dose changes for 14 days and do not intend to change the dose will be eligible. Those who have been on the antidepressant for less than 14 days or intend to have their medication optimized will be asked to wait for screening until they meet the 14-day criterion
- 3.2.5 Has used any of the IntelliCare apps more than one time in the last 3 months.

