#### 4.3 Data

- **4.3.1.1.1** *Adherence:* The primary adherence outcome will be length of time from initiating treatment to last use of treatment elements. We will also explore the motivational system by examining the number of motivational messages delivered, number viewed and the ratio of viewed/delivered by treatment arm. More specifically:
- **4.3.1.1.1.1** Messages include text and email messages between participants and study staff for the purposes of coaching and participant management.
- **4.3.1.1.2** App use includes the number, timing, and duration, application launches and launches of specific pages within the app.

- **4.3.1.1.2** *Depression:* Primary patient centered outcomes will use continuous measures of depression and anxiety.
- **4.3.1.1.2.1** *PHQ-9* will be used to evaluate self-reported depression. GAD-7 will be used to evaluate self-reported anxiety.
- **4.3.1.1.3** *Secondary Outcome Measures* will include the following (for a full list of self-report measures see Measures Appendix):
- **4.3.1.1.3.1** *Satisfaction*, measured using the USE questionnaire, which was designed to measure satisfaction, usefulness, ease of use, and ease of learning.

*Moderators and mediators* will include the measures provided prior to initiating treatment the Mini International Neuropsychiatric Interview, the SCT Motivation assessment, Behavioral Activation, wellbeing and quality of life, Coping, and

**4.3.1.1.3.2** Audiofiles include audio recordings of coaching and assessments. Audio files may be transcribed by one or more of the following NU transcription vendors:

GMR Transcription https://www.gmrtranscription.com/

Wordsworth https://wordsworthcoop.com

Files may be shared via secure access to FSM servers or through vendors' proprietary web-based applications for secure file management.

- **4.3.1.1.4** Coach generated notes on participant encounters.
- 4.4 Removal of Subjects from Study

Patients can be taken off the study treatment and/or study at any time at their own request, or they may be withdrawn at the discretion of the investigator for safety, behavioral or administrative reasons. The reason(s) for discontinuation will be documented and may include:

- 4.4.1 Patient voluntarily withdraws from treatment (follow-up permitted);
- 4.4.2 Patient withdraws consent (termination of treatment and follow-up);
- 4.4.3 Patient is unable to comply with protocol requirements; (termination of treatment and follow-up);

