### **6** STATISTICAL CONSIDERATIONS

- **6.1** Public Deployment
- **6.2** Adherence Outcomes:
- 6.3 The primary outcome of Phase 1a will be rate of usage of each Intellicate application. This will be

examined by calculating standard descriptive statistics for the number of downloads and launches of each application. Secondary analyses of the primary outcome will include comparisons of co-usage of Intellicare application pairs, which we will test using Pearson correlations.

- **6.4** Field Trial
- **6.5** Power/sample size:
- 6.5.1 We estimate that we will have a 20% dropout, which will give us 80% power to detect effect sizes of 0.30. Power calculations were performed using Pass 2008.(Hintze, 2008)
- **6.6** Adherence Outcomes:
- 6.6.1 The primary outcome will be time to last use of a treatment element (lesson or tool), and will be tested between groups using traditional survival (Kaplan-Meier) methods, where the event of interest is last use from intervention start. Secondary analyses of the primary outcome would include Cox regression models that would adjust for potential effect modifiers or moderators such as gender, race, and age.
- **6.7** Patient Centered Outcomes:
- 6.7.1 Although power was presented for independent t-tests, primary analyses for patient centered outcomes (PHQ-9 and GAD-7) will utilize dependent t-tests
- **6.8** Mediation Analyses:
- 6.8.1 Mediators, such as app usage, we be examined in mediation models as time-varying covariates. We used the framework of Muller and colleagues(Muller, Judd, & Yzerbyt, 2005) to identify those variables, which mediate the effects of treatment on depression and anxiety. Only if the 4 criteria specified by Muller are satisfied (treatment effect for depression, treatment effect for the mediator, effect of mediator on depression, and reduction of treatment effect when mediator is included), will we calculate the effect of mediation using MacKinnon and colleagues' product of coefficients method.(MacKinnon, Lockwood, Hoffman, West, & Sheets, 2002) Bias-corrected 95% confidence intervals for the mediated effect will be calculated using bootstrapping.(Shrout & Bolger, 2002)
- 6.8.2 Development of the recommendation engine algorithms will use machine learning and Baysean. statistical methods that will continuously learn that will continuously learn from user interactions with IntelliCare to provide intervention recommendations.
- **6.9** Randomized Control Trial
- **6.9.1** Power/sample size:

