#### **6.10** Adherence Outcomes:

- 6.10.1 The primary outcome will be time to last use of a treatment element (lesson or tool), and will be tested between groups using traditional survival (Kaplan-Meier) methods, where the event of interest is last use from intervention start. Secondary analyses of the primary outcome would include Cox regression models that would adjust for potential effect modifiers or moderators such as gender, race, and age.
- **6.11** Patient Centered Outcomes:
- 6.11.1 Although power was presented for independent t-tests, primary analyses for patient centered outcomes (QIDS-C, MDD, and PHQ-9) will utilize generalized linear mixed (GLM) models (with link functions depending on the distribution of the outcome), that can examine patterns over the course of treatment and follow-up, and can account for missing data.(Gibbons et al., 1993)
- **6.12** Secondary Mediation Analyses:
- 6.12.1 Mediators will be entered into our models as time-varying covariates. We used the framework of Muller and colleagues(Muller, Judd, & Yzerbyt, 2005) to identify those variables, which mediate the effects of treatment on depression. Only if the 4 criteria specified by Muller are satisfied (treatment effect for depression, treatment effect for the mediator, effect of mediator on depression, and reduction of treatment effect when mediator is included), will we calculate the effect of mediation using MacKinnon and colleagues' product of coefficients method.(MacKinnon, Lockwood, Hoffman, West, & Sheets, 2002) Bias-corrected 95% confidence intervals for the mediated effect will be calculated using bootstrapping.(Shrout & Bolger, 2002)
- 6.12.2 Development of the recommendation engine algorithms will use machine learning and Baysean. statistical methods that will continuously learn that will continuously learn from user interactions with IntelliCare to provide intervention recommendations.
- **6.12.3** Exploration of moderating variables on outcomes, such as baseline demographics, baseline characteristics.
- 2.2.3 Explore, optimize, and validate coaching methods. This will include analyses of all data captured in the delivery of coaching, including the timing and content of messages and phone calls, and coach records related to participant encounters.

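### The RCT outcome list in 6.11.1 omits GAD-7, so the anxiety part of both hypotheses has no stated between-group analysis, and it names two outcomes that 4.1.6.1 does not schedule after baseline

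*Combined protocol and SAP*

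**What the plan says.** Objective 2.1.3 states: "The primary patient centered outcome will be depression/anxiety severity". The first hypothesis is that "IntelliCare with the recommendations, in contrast to IntelliCare without the recommendations, will produce greater adherence and greater reductions in depressive and anxiety symptoms", and the second that "IntelliCare with coaching will produce greater greater adherence and greater reductions in depressive and anxiety symptoms". Section 4.3.1.1.2 adds: "Primary patient centered outcomes will use continuous measures of depression and anxiety". Section 4.3.1.1.2.1 assigns PHQ-9 to depression and says that "GAD-7 will be used to evaluate self-reported anxiety". Section 4.1.6.1 schedules both questionnaires at baseline, weeks 4 and 8, and 3 and 6 months after treatment.

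The RCT analysis statement, 6.11.1, reads: "primary analyses for patient centered outcomes (QIDS-C, MDD, and PHQ-9) will utilize generalized linear mixed (GLM) models". Its counterpart for the field trial, 6.7.1, reads: "primary analyses for patient centered outcomes (PHQ-9 and GAD-7) will utilize dependent t-tests".

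**The concern.** The three outcomes listed in 6.11.1 are all depression measures. Anxiety is half of the pair that defines the primary patient-centered outcome, and it appears in both hypotheses. Eligibility criterion 3.1.1 ("Meets criteria for clinically significant symptoms of depression and or anxiety using self-report measures") also lets a participant enter with anxiety symptoms alone. For such a participant, PHQ-9 may not be the measure on which benefit is expected.

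If the list is taken at its word, the trial could be analysed in full compliance with 6.11.1 without ever comparing the groups on anxiety. A favourable GAD-7 result could then be challenged as not pre-specified, and an unfavourable one could go unreported without departing from the plan.

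The list has a second fault. Two of its three entries, QIDS-C and MDD, do not appear as repeated outcomes in the RCT assessment section, whereas a mixed model over treatment and follow-up needs repeated measurements.

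**Working it through.** **1. Definition against analysis list.**

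| Measure | Defines the primary patient-centered outcome (4.3.1.1.2, 4.3.1.1.2.1) | Scheduled as an RCT outcome (4.1.6.1) | Listed in 6.11.1 |
|---|---|---|---|
| PHQ-9 | yes | 5 time points | yes |
| GAD-7 | yes | 5 time points | no |
| QIDS-C | no | not listed | yes |
| MDD (MINI MDE module) | no | baseline only | yes |

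Section 6.11.1 therefore names 1 of the 2 defining measures. Anxiety is in 2 of 2 hypotheses, but neither GAD-7 nor anxiety is mentioned anywhere in 6.9 to 6.12.

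**2. Could another section supply the GAD-7 comparison?** The only analysis statement that names GAD-7 is 6.7.1. It concerns the field trial, which 4.1.3 describes as single arm, and it uses a within-person t-test. It cannot compare randomized groups. The moderator line in 6.12.3 is exploratory and names no outcome.

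**3. QIDS-C and MDD.** The RCT baseline interview in 4.1.5.3 names the MINI only, while the field-trial interview in 4.1.3.1 names the MINI, HAM-A and QIDS. On the other side, 4.1.6.1 says that assessments include telephone interviews, and 4.4.5 refers to QIDS-C and MINI at later assessments for suicidality monitoring. The sections conflict and do not settle whether these measures exist after baseline.

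**4. Does adding GAD-7 disturb the stated power?** Inputs from 6.9.2: 135 per arm, effect size 0.34, independent t-test, 80% power. The 5% type 1 error rate is stated there for the log-rank test; using it two-sided for the t-test is an assumption.

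Formula (normal approximation): power = Φ(d·√(n/2) − z), with z the two-sided critical value.

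- The plan's own figure: 0.34 × √67.5 = 2.793; 2.793 − 1.960 = 0.833; Φ = 79.8%. The noncentral t gives 79.5%, with a detectable effect of 0.342 at 80% power. The stated figure reproduces.
- GAD-7 at the same unadjusted 5%: the same result, because the calculation depends only on the standardized effect.
- Illustration, alpha split equally (0.025 each): 2.793 − 2.241 = 0.552; Φ = 71.0%. The noncentral t gives 70.5%, with a detectable effect of 0.377.

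The documents do not call for a split. The last line shows only why the status of the two measures needs to be stated.

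**The case against.** The best defence is that the bracketed list is simply out of date. Section 6.11.1 stands under the heading of patient-centered outcomes, which 4.3 defines to include GAD-7. Section 6.9.2 powers continuous patient-centered outcomes as a class. Section 6.11.1 gives one model family for that class, so the analyst would know to fit the same mixed model to GAD-7. In addition, the study summary and 6.10.1 make adherence the primary outcome of the trial.

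Much of this stands, and it rules out some stronger readings:

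- A reader might infer that the sponsor decided not to test anxiety, or that the choice of GAD-7 model is wide open until the data are seen. The documents do not support either. The model family is evident; what is open is whether GAD-7 is included and with what status.
- A reader might infer that PHQ-9 is fully specified by comparison. It is not. Section 6.11.1 spells out no between-group contrast for any outcome, so adding GAD-7 to the brackets alone would not be enough.
- A reader might infer that QIDS-C and MDD cannot be analysed. Section 4.4.5 prevents that conclusion; the sections are in conflict, and no more can be said.

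What does not stand is the suggestion that nothing needs changing. The list in 6.11.1 is explicit and is not introduced as a set of examples, although the protocol marks examples as such elsewhere (2.2.1, 4.1.6). The parallel field-trial sentence does name GAD-7. A pre-specified test of part of both hypotheses should not rest on inference from another section.

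**Conclusion.** The outcome list in 6.11.1 is wrong as written. It conflicts with 2.1.3, 4.3.1.1.2, 4.3.1.1.2.1 and 4.1.6.1: it leaves out one of the two measures that define the primary patient-centered outcome and, read literally, leaves the anxiety part of both hypotheses untested. The QIDS-C and MDD entries also lack support in the RCT outcome schedule, though the documents leave open whether they are collected.

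The consequence is limited. The primary adherence outcome is unaffected, PHQ-9 remains in the list, and the data needed for GAD-7 are already planned. The statement that the power figure carries over to GAD-7 assumes an unadjusted two-sided 5% and a standardized effect of 0.34 on GAD-7; under an equal split of alpha, power would be about 70%.

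This conclusion rests on a comparison of the current sections, and the arithmetic only confirms that no stated figure has to change at an unadjusted 5%.

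**What to change.** In 6.11.1:

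1. Name PHQ-9 and GAD-7 as the primary patient-centered outcomes, each analysed with the mixed model already planned over the five time points in 4.1.6.1.
2. State the between-group contrast, the same for both measures.
3. State whether the two are co-primary or separately tested and, if separately tested, how the type 1 error is handled. If alpha is divided, restate the power in 6.9.2.
4. Remove QIDS-C and MDD from the list, or reconcile the list with 4.1.6.1 and label them as other than the primary continuous measures.

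Items 1 to 3 are wording edits and need no new data, apart from a revised power sentence if alpha is divided. Item 4 needs a sponsor decision. Removal is a wording edit; keeping the two measures needs a schedule entry in 4.1.6.1 and, if they are not already administered after baseline, additional interviews.

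Two neighbouring matters should be handled separately. The assessment weeks and instruments in 4.4.5 must be reconciled with 4.1.6.1 and 4.1.3.3; no view is taken here on which is right. The RCT mediation text in 6.12.1 mentions depression only, whereas objective 2.2.1 covers depression and anxiety.

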# PHASE 3 RANDOMIZED CONTROLLED TRIAL

- 4.1.4 Phase III Randomized Controlled Trial. For the RCT, 300 participants meeting entry criteria will be enrolled over 13 months (approximately 23 per month). Participants will be randomized using a factorial design with the following factors:
- **4.1.4.1** Factor 1. Hub App with intelligent recommender system/Hub app without intelligent recommender system: This factor is consistent with Objective 2.1.3 on pg. 4
- **4.1.4.2** Factor 2. Coaching/No Coaching: This factor would allow us to examine and control for the effect of coaching.
- **4.1.5** *Phase III Enrollment.* Participants in the RCT will be enrolled remotely to avoid excluding individuals with access barriers who are among those who would be likely end users. Screening will be conducted in 3 stages.
- 4.1.5.1 Screening Stage 1 (pre-consent): Interested parties will complete a brief web screen to determine whether there is any reasonable expectation that they might be eligible (data from the brief screen will be included in the study dataset). If they are clearly not eligible they will be informed of this and thanked. If they appear to be eligible a research assistant will follow-up by phone to clarify responses from the web screen and ask additional phone screening questions. If the participant passes the stage 1 phone screen s/he will be invited to initiate the online consent process and proceed to screening stage 2 described below.

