At the end of the 8 week intervention, all participants will be informed that they may continue using the IntelliCare system on their phones but participants in groups 1 and 3 will no longer have access to their coach. For any participants who do continue app use after the study period has ended, the IntelliCare system will continue to collect app data as before.

4.1.6.1 Phase III Assessment, measures and compensation. RCT participants will receive trial assessments at baseline, week 4, and week 8 (post-treatment). Post-treatment follow-up evaluations will occur at 3 and 6 months to evaluate maintenance of gains. Assessments will consist of telephone based interviews and online self-report questionnaires. All assessments and evaluations will be conducted by an RA (i.e. coaches will not perform assessments on patients they coach). Depression will be measured at baseline by telephone interview using the MINI MDE module. Self-reported depression will be measured at baseline, wk4, wk8, 3 months post-treatment and 6 months post-treatment using the PHQ-9 administered online. Self-reported anxiety will be measured using the GAD-7 administered online at

baseline wk4, wk8, 3 months post-treatment and 6 months post-treatment. *Adherence* will be assessed through app use data from phone, including number of times the apps were accessed, number of times each app feature was accessed and percentage of messages viewed. Participants will be paid up to \$40 for the screening/baseline assessments, \$30 for the week 4 and 8 assessments, and \$30 for the 3 and 6 month assessments (total= up to \$160). Participants will not be compensated for using the apps or communicating with the study coach. Payments may be made in either Amazon credits or by check depending on participant preference, NU payment policies, and payment availability at the time of study participation. Individuals recruited through Focus Pointe Global will be paid through PayPal by Focus Pointe Global.

**4.1.7** *Phase II Study Retention.* Communication from the research study may occur across a participant's involvement in the trial to increase participant retention. Such contact could include sending greeting cards via mail or email (thank you, birthday, etc.) or sending small tokens of appreciation (keychains, pens, stress balls).

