- 6.9.2 Preliminary data indicates that approximately 50% of patients stop participating in BITs (which we define here as "drop out") by week 7 (see Sec. D.1.1). A sample size of 135/arm (total sample of 270) will provide 80% power to detect a difference in median drop out time from 7 to 10 weeks. We estimate from existing data (Sec D.1.1) that a 3 week increase would result in an 11% improvement in depression severity (ES=0.30). Additionally, this sample provides 80% power to detect an increase in continued participation from 50% to 61.6% at week 7. Both analyses are based on a log-rank test at a type 1 error rate of 5%, with accrual of 54 weeks and 12 weeks of intervention. Power for continuous patient

centered outcomes were based on independent t-tests, and would have 80% power to detect effect sizes of 0.34. Power calculations were performed using Pass 2008.(Hintze, 2008)

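### Section 6.11.1 does not state that the RCT mixed model adjusts for the baseline score, although baseline PHQ-9 and GAD-7 are collected before randomisation

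*Combined protocol and SAP*

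**What the plan says.** Section 6.11.1 is the whole stated analysis of the RCT patient-centered outcomes. It acknowledges that power was computed for t-tests, then plans generalized linear mixed models "that can examine patterns over the course of treatment and follow-up, and can account for missing data". The outcomes it lists are QIDS-C, MDD and PHQ-9. It names no covariates, no role for the baseline score, no time point for the contrast and no covariance structure.

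Section 4.1.6.1 gives the schedule: "Self-reported depression will be measured at baseline, wk4, wk8, 3 months post-treatment and 6 months post-treatment using the PHQ-9 administered online". GAD-7 follows the same schedule. Sections 4.1.5.2 and 4.1.5.3 place the baseline questionnaires before randomisation. Section 4.3 treats the continuous depression and anxiety measures, PHQ-9 and GAD-7, as the primary patient-centered outcomes.

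On power, Section 6.9.2 says "A sample size of 135/arm (total sample of 270) will provide 80% power" for the drop-out comparison. It adds that the continuous outcomes were "based on independent t-tests, and would have 80% power to detect effect sizes of 0.34". The same section expects a three-week gain in participation to correspond to an effect size of 0.30 on depression severity.

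The only covariate adjustment named for the RCT is in the secondary Cox models for adherence (Section 6.10.1: gender, race, age). Baseline characteristics appear otherwise only as exploratory moderators (Sections 2.2.2 and 6.12.3).

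**The concern.** A pre-randomisation measurement of the outcome itself is usually the most useful covariate available, and here it costs nothing. A plan that names only a mixed model can be carried out in several ways that use that measurement differently:

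- compare groups at follow-up and ignore baseline;
- put baseline in as the first repeated response, let its mean differ by group, and test group by time, which amounts to comparing change scores;
- adjust for baseline, either as a covariate or by constraining the baseline means to be equal.

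The third is the most precise of these at a given follow-up visit. The choice matters in this trial because the stated detectable effect (0.34) is larger than the expected one (0.30). The first two options also let part of any chance baseline imbalance between hub or coaching levels into the estimate. If the choice is left open, the model can be settled after the data are seen.

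**Working it through.** **Inputs.** From Section 6.9.2: 135 per arm, read here as per level of each factor; 80% power; detectable effect 0.34; expected effect 0.30 on depression severity. The 5% type 1 error in 6.9.2 is stated for the log-rank analyses, and I assume the same for the t-test. The baseline to week-8 correlation r is not in the documents. It is assumed, with a range of 0.3 to 0.7. SDs are taken as equal at the two visits.

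**Step 1: reproduce 0.34.** The two-sided normal approximation gives (1.960 + 0.842) × √(2/135) = 0.341. The exact t calculation gives 0.342. A one-sided test would give 0.303, so the stated figure is two-sided and it reproduces. Unadjusted power at an effect of 0.30 is 69%.

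**Step 2: variance of the treatment contrast at one follow-up visit**, relative to an unadjusted comparison:

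- baseline as covariate, or baseline means constrained equal: 1 − r²;
- unconstrained group-by-time (change): 2(1 − r).

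With two time points and complete data, the constrained longitudinal model and the covariate model have the same variance.

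**Step 3: results at 135 per level.** The detectable effect is 0.342 times the square root of the factor. Power is from the t calculation with 0.30 divided by that square root.

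| r | 1 − r² | Adjusted: detectable effect | Adjusted: power at 0.30 | 2(1 − r) | Change: detectable effect | Change: power at 0.30 |
|---|---|---|---|---|---|---|
| 0.3 | 0.91 | 0.326 | 73% | 1.4 | 0.405 | 55% |
| 0.4 | 0.84 | 0.314 | 76% | 1.2 | 0.375 | 61% |
| 0.5 | 0.75 | 0.296 | 81% | 1.0 | 0.342 | 69% |
| 0.6 | 0.64 | 0.274 | 87% | 0.8 | 0.306 | 78% |
| 0.7 | 0.51 | 0.244 | 93% | 0.6 | 0.265 | 89% |

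**Step 4: when does adjustment reach 0.30?** Solving 0.342 × √(1 − r²) = 0.30 gives r = √(1 − (0.30/0.342)²) = 0.48. Starting from the rounded 0.34 gives 0.47.

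**Step 5: is adjustment ever worse?** The factor 1 − r² is below 1 for any non-zero r. The ratio of the change factor to the adjusted factor is 2(1 − r)/[(1 − r)(1 + r)] = 2/(1 + r), which exceeds 1 for every r below 1. It is 1.54 at r = 0.3, 1.33 at r = 0.5 and 1.18 at r = 0.7. In terms of participants, adjustment is worth between 54% and 18% more than the change contrast over that range.

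**Step 6: baseline imbalance.** A chance baseline difference d shifts an unadjusted follow-up comparison by r·d and a change comparison by −(1 − r)·d. The shift is partial in both cases and opposite in sign.

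**The case against.** The strongest reply is that 6.11.1 is silent and does not exclude adjustment. A reader might infer that the plan forgoes it, but the text does not say so. A longitudinal model may already carry baseline as its first response, and with a common baseline mean that recovers the full gain in Step 3. This stands: the defect is an unspecified model, and no loss has been shown. It does not remove the point, because the same wording equally permits the two less precise versions.

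Second, the unadjusted t-test is the basis for power and not the planned analysis, and no section fixes week 8 as the contrast. A contrast averaging the four post-baseline visits could do better without a covariate. Under compound symmetry with r = 0.4, the mean of four visits minus baseline has factor (1 − 0.4)(1 + 1/4) = 0.75, giving 0.342 × √0.75 = 0.296. So the single-visit figures cannot be assigned to this plan as its actual loss. Adjustment still helps in that setting. The mean of four visits has variance (1 + 3 × 0.4)/4 = 0.55; adjusted for baseline this is 0.55 − 0.16 = 0.39, giving 0.342 × √0.39 = 0.214.

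Third, "For the RCT, 300 participants meeting entry criteria will be enrolled over 13 months", which is 150 per factor level, and no section says that 270 will be analysed for these outcomes. At 150 per level the unadjusted detectable effect is 0.3245 and power at 0.30 is about 74%. Adjustment then reaches 0.30 at r = √(1 − (0.30/0.3245)²) = 0.38. The gap narrows, but the ordering of the three analyses does not change.

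Fourth, a reader might argue that entry on depression, anxiety or both spreads baseline scores and so makes r large. The documents give neither a baseline SD nor a correlation, and requiring clinically significant symptoms restricts the range on at least one scale. The argument cannot fix r.

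**Conclusion.** The point holds as a specification gap with a free gain in precision. Section 6.11.1 should say how baseline enters. Of the analyses it leaves open, the baseline-adjusted one is the most precise at a given visit for any r strictly between 0 and 1.

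The size is conditional. At 135 per level and r = 0.5, adjustment removes 25% of the variance, lowers the detectable effect from 0.342 to 0.296 and raises power at 0.30 from 69% to 81%. At r = 0.3 or 0.4 the detectable effect stays above 0.30. It would therefore go too far to say that the plan gives up a quarter of the variance, or that adjustment brings the trial to its expected effect. Both statements need r of about 0.48 to 0.5, which the documents do not supply.

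Two limits of scope apply. Section 6.11.1 lists PHQ-9 and not GAD-7, so its wording bears directly on PHQ-9 only; GAD-7 is a primary patient-centered measure without a stated RCT model. The 0.30 is given for depression severity following a gain in participation, so it is no benchmark for GAD-7 and is not stated for the coaching factor. This concerns efficiency and pre-specification. It does not make the comparison invalid, since randomisation protects the unadjusted and change contrasts from systematic bias.

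**What to change.** In Section 6.11.1, state that PHQ-9 and GAD-7 are each modelled over the post-baseline visits with that scale's own baseline score as a covariate. Alternatively, specify a longitudinal model that includes baseline as a response, with its mean constrained equal across randomised groups. State that the hub and coaching contrasts are estimated at week 8 from that model. In Section 6.9.2, report the adjusted detectable effect beside the 0.34, with the assumed r and a range.

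The cost is a sentence or two in 6.11.1 and one figure in 6.9.2. No data, visits or participants are added. Phase II measures PHQ-9 and GAD-7 at baseline and week 8 (Section 4.1.3.3), so the field trial could supply an estimate of r.
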